1.4.1. Calculation formulas

| Product | Placebo |
|--|--|
| $\Delta Pdt = (Pdt_{ti} - Pdt_{t0})$ | $\Delta Pla = (Pla_{ti} - Pla_{t0})$ |
| $\Delta\% Pdt = \frac{(Pdt_{ti} - Pdt_{t0})}{Pdt_{t0}} \times 100$ | $\Delta\% Pla = \frac{(Pla_{ti} - Pla_{t0})}{Pla_{t0}} \times 100$ |
| $\Delta\Delta = \Delta Pdt - \Delta Pla$ | |
| $\Delta\Delta\% = \Delta\% Pdt - \Delta\% Pla$ | |

with:
 Pdt: value obtained on the zone treated by the tested product
 Pla: value obtained on the zone treated by the placebo
 t0: before product application
 ti: at each measurement time after product application

1.4.2. Statistical method

Only descriptive analysis (Mean, SEM, frequency...) is calculated.

1.4.3. Statistical software

The software used is EXCEL.

1.5. AUDIT AND TRIAL MONITORING VISIT

An audit and/or trial monitoring visit may be carried out at the Sponsor's request or by the appropriate regulatory authority. The aim of the monitoring visit is to verify that the study is conducted according to the determined protocol and current regulations.

2. PRINCIPLES AND RESULTS

2.1. STANDARDIZED PHOTOGRAPHS

A standardized photograph of each lesion will be taken on the visits D0, M1, M2, M3 and M4.

The following parameters will remain fixed from one visit to another:

- Ambient lighting (use preferably a blind room without window).
- Setting the camera (speed and diaphragm).
- Distance device / lesion: constant.
- Position device / lesion: constant (perpendicular axis of the lens to the lesion).

The person in charge of the photographs will have to photograph the identification of the patient and the visit, for example on the heading of the data collection notebook or on a printed card for this purpose.

2.2. ANALYSIS OF THE LESIONS SURFACE

2.2.1. Principle

On each visit, the perimeter of each target lesion and any possible repigmentation ranges inside it will be traced and identified on a tracing sheet. Natural marks such as scars, moles, tattoos or others will also be reported on the tracing sheet in a manner to find the target lesions easily.

An entire body drawing, front view and back view, must be present in the data collection notebook so that the lesions can be represented and numbered. The number of each lesion must also appear on the tracing sheet.

The surface measurement of each lesion (in cm²) will be made by the Sponsor, by image analysis of the tracing sheet under a video camera using a classical image analysis software.

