| Objectives | 
Primary objective:
 
 • Evaluate the percentage of repigmentation observed one month after the end of three months of treatment measured on an objective layer by image analysis; 
Secondary objectives: Evaluate:
 
 • the percentage of repigmentation observed after one, two and three months of treatment measured on an objective layer by image analysis; • the ability of the product to maintain the human body in good condition (cutaneous acceptability) by clinical examination by the dermatologist; • Patient satisfaction using a visual analogue scale from 0 to 10. • The illustrative effect using standardized photographs; • The quantity of product by weighing the tubes. • The occurrence of possible adverse effects. | | | | | | | | | | | | | | | | | | | | | | | | | | | | | | | | | | | | | | | | | | | | | | | | | | | | | | | | | | | | | | | | | | | | | | | | | | | | | | | | | | | | |
|---|--|---------|-----------------|---------|---------|-------|----|----|-------------------|---|---|---|---|---|---|---|---|---|---|---|---|---|--|---|---|---|---|---|---|--|---|---|---|---|---|---|---|---|---|---|---|---|---|---|---|---|---|---|---|---|---|---|---|---|---|---|---|---|---|---|---|---|---|---|-------------------------------|---|---|---|---|---|---|--|----------|---------|---------|---------|---------|-------|--|----------|---|---|---|---|-------|
| | 
 • Study in proof of concept; • Double blind study; • Comparative study, versus placebo in intra-individual; • Three parallel groups testing different dosages / combinations of treatments; • Randomized. | | | | | | | | | | | | | | | | | | | | | | | | | | | | | | | | | | | | | | | | | | | | | | | | | | | | | | | | | | | | | | | | | | | | | | | | | | | | | | | | | | | | |
| Methodology | | | | | | | | | | | | | | | | | | | | | | | | | | | | | | | | | | | | | | | | | | | | | | | | | | | | | | | | | | | | | | | | | | | | | | | | | | | | | | | | | | | | | |

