1.3. STUDY STAGES

BEFORE THE BEGINNING OF THE STUDY

Technician:

- weighs the study products before their use.

Twice a week:

Patients of both groups A and B come to the hospital where the lesions will be exposed with a Quantel 308 excimer lamp that delivers a narrow UVB spectrum centered of a wavelength of around 308nm. This lamp makes it possible to perform phototherapy localized on the target lesion. Fluences will be performed twice a week throughout the duration of the study.

ON D0**Patients:**

- come to the investigation center without having applied any product to the body since the previous evening;
- are informed about the trial objectives, the procedures and the risks of the study with the information sheet;
- sign two copies of the Consent Form.

Dermatologist:

- verifies inclusion and non-inclusion criteria;
- performs a standardized photo of each target lesion;
- traces and identifies the perimeter of each target lesion (1 to 3 on each side) on a tracing sheet (the natural marks such the scars, moles, tattoos or others will be also reported on the tracing sheet in order to easily find the target lesions);
- performs a clinical examination of the skin on the application area;
- asks the subjects about their usual unpleasant sensations;
- explains to the subjects the product application conditions and frequency;
- gives to the subjects:
 - the product to be used according to the instructions in 2.1.2 and 2.2.2,
 - the daily log to write down their possible unpleasant sensations or medications,

ON M1 (last application being done the previous day)**Subjects:**

- return to the hospital with no product applied to the body since the previous evening;
- bring back their daily log;

Dermatologist:

- performs a standardized photo of each target lesion;
- traces and identifies the perimeter of each target lesion (1 to 3 on each side) on a tracing sheet (the natural marks such the scars, moles, tattoos or others will be also reported on the tracing sheet in order to easily find the target lesions);
- performs a clinical examination of the skin on the application area;
- asks the subjects about the unpleasant sensations they felt during the study and assesses the cutaneous acceptability of the study product;
- collection of the concomitant treatments and undesirable effects.

On M2 (the last application being done the previous night):**Subjects:**

- return to the hospital with no product applied to the body since the previous evening;

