6.3. CONFIDENTIALITY AND GENERAL DATA PROTECTION REGULATION

In this study, DermScan processes personal data of subjects on behalf of the Sponsor, in accordance with the rules on the protection of personal data. For this purpose, EUROFINS DermScan/Pharmascan limits the collection and use of personal data to that which is needed for analysis and control purposes, by insuring their security and integrity and by guaranteeing their confidentiality.

DermScan makes sure beforehand and throughout the duration of the data-processing:

- of the compliance with the obligations of the applicable data protection law,
- to inform subjects of their personal data-processing after obtaining their consent,

- to implement and maintain appropriate technical and organisational measures.

An identification code is attributed to each subject for the purpose to keep his/her identity confidential. This code consists of: the first two letters/first letter of the subject's name and the first letter of his/her first name.

According to Article 14 of GDPR, the concerned subject must be informed of the identity and the contact details of the Controller and, where applicable, of the controller's representative. However, considering the objective of the study, to avoid any bias in the investigational product evaluation, the identity of the Sponsor is not revealed to the subject participating.

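### The Sponsor measures the primary endpoint from numbered tracing sheets in a study called double blind, and the protocol does not state that this reading is masked to subject, side, visit or allocation

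*Combined protocol and SAP*

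**What the plan says.** The synopsis states the primary objective as: "Evaluate the percentage of repigmentation observed one month after the end of three months of treatment measured on an objective layer by image analysis". The image analysis is described in section 2.2.1: "The surface measurement of each lesion (in cm²) will be made by the Sponsor, by image analysis of the tracing sheet". No second or independent reader is named.

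On the sheets themselves, section 1.3 has the dermatologist do the drawing: at each visit the dermatologist "traces and identifies the perimeter of each target lesion (1 to 3 on each side) on a tracing sheet". Section 2.2.1 adds that repigmented areas inside the perimeter and natural skin marks are also drawn, and that "The number of each lesion must also appear on the tracing sheet". The key to those numbers is a front and back body drawing, which "must be present in the data collection notebook so that the lesions can be represented and numbered".

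On blinding, the synopsis says "Double blind study" and names no blinded roles. Section 1.2.1 lists both products as encoded, in the same form and packaging. Section 1.2.5 randomizes the right or left side within each subject. Appendix 5.1 prints the list: 12 IDs, each with its group and with Produit A or B for each side. The product lot is 120918A and the placebo lot 120918B.

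**The concern.** In an intra-individual comparison, everything depends on the two sides being measured alike. Here the last step before the number exists is performed by the party that supplies the product. The protocol does not say what that reader may see: it describes no coding of sheets, random reading order or withholding of the allocation list.

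The dermatologist's outline limits the reader's freedom but does not remove it. No rule says whether the inner or outer edge of a drawn line is the boundary, or how split or merged patches are handled. If those choices followed a known allocation, they would go straight into ΔΔ%. With 4 patients per group and a descriptive analysis only (section 1.4.2), each patient is a quarter of a group mean, so a few such readings would be visible in the result.

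**Working it through.** The plan gives no power, alpha, effect size or measurement error, so there is no figure of its own to reproduce. The check has four parts.

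**1. What the reader needs to break the blind.** Section 1.4.1 defines Δ% for each side as 100 × (area at ti − area at t0) / area at t0, and ΔΔ% = Δ% product − Δ% placebo. Each value must therefore be linked to subject, side and visit at some point. The protocol does not separate that linking from the Sponsor's reading.

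Tally of Appendix 5.1, Produit A on the right side:
- Group A (IDs 1, 4, 5, 8): IDs 1 and 8, so 2 of 4.
- Group B (IDs 2, 6, 7, 12): IDs 6 and 12, so 2 of 4.
- Group C (IDs 3, 9, 10, 11): IDs 3 and 10, so 2 of 4.
- Total: 6 of 12.

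Side alone is thus uninformative (50/50). Subject ID, side and the list together give the A/B code for every lesion. Turning the code into product or placebo needs one more fact. The lot suffixes suggest it, but the documents do not say that Produit A and B follow them.

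**2. Effect of a side-dependent error (assumed values).** Let a fraction r of the D0 area truly remain at M4 on both sides, with D0 read correctly. Suppose the product side is under-read and the placebo side over-read by a proportion e.

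False ΔΔ% = 100 × [r(1 − e) − r(1 + e)] = −200 × r × e.

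Example with r = 0.70 and e = 0.05:
- Product: 0.70 × 0.95 = 0.665, so Δ% = −33.5.
- Placebo: 0.70 × 1.05 = 0.735, so Δ% = −26.5.
- ΔΔ% = −7.0 points, where the truth is 0.

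| Assumed e | r = 0.50 | r = 0.70 | r = 0.90 |
|---|---|---|---|
| 2% | −2.0 | −2.8 | −3.6 |
| 5% | −5.0 | −7.0 | −9.0 |
| 10% | −10.0 | −14.0 | −18.0 |

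Negative values favour the product.

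**3. Effect of knowing only the visit.** If both sides are under-read at M4 by the same e, each Δ% shifts by −100 × r × e. At r = 0.70 and e = 0.05 that is −3.5 points per side. With no true difference the shifts cancel and ΔΔ% moves by 0.

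**4. Effect of the edge choice (assumed circular lesion and 1 mm line).** For area S, radius = √(S/π), and outer-edge minus inner-edge area relative to S is 0.2 / radius (in cm).
- S = 2 cm²: radius 0.798, difference 25.1%.
- S = 100 cm²: radius 5.642, difference 3.5%.

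These are the size limits in section 1.1.1. The difference enters in full only if the reader changes edge between sheets. With one edge throughout, a 2 cm² circle shrinking to 70% has radii of 0.798 and 0.668 cm:
- Inner edge: (0.618 / 0.748)² = 0.682, so Δ% = −31.8.
- Outer edge: (0.718 / 0.848)² = 0.716, so Δ% = −28.4.

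The gap is 3.4 points, and it largely cancels in ΔΔ% if both sides are read the same way.

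**The case against.** A reader might infer that the Sponsor measures each surface knowing its side and visit. The documents do not support that. Section 2.2.1 requires only the lesion number on the sheet, and the key to location is in the data collection notebook, which is not said to go to the reader. Visit identification is required only for the photographs, where the photographer "will have to photograph the identification of the patient and the visit".

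It is equally tempting to say that the blind covers only subject and investigator. The synopsis names no roles, so the reader is neither shown to be outside the blind nor stated to be inside it.

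Three further limits stand:
- Side is not treatment, as the 6 of 12 tally shows.
- The dermatologist decides at the site what is repigmented, before the Sponsor measures.
- The 25% edge figure is an extreme: the smallest lesion, an assumed line width and a change of edge.

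Section 6.3 should not be read as an admission of Sponsor measurement bias. Its wording, "to avoid any bias in the investigational product evaluation, the identity of the Sponsor is not revealed to the subject participating", concerns what subjects are told.

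Finally, this is a descriptive proof-of-concept study, so one could treat the matter as a request for clarification. That argues for a light remedy. It does not remove the gap, because a plan that claims double blinding should state who is blinded at the step that produces the primary number.

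**Conclusion.** The concern holds in this form: the Sponsor reads the primary endpoint from numbered sheets, no masking of that reading is stated, and the list of IDs, sides and codes is printed in the protocol. Following the plan as written would leave the blind open at this step. Nothing in the documents shows that it was broken or that any reading was biased.

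The harm to the placebo-controlled result depends on the reader having subject ID, side, list and the meaning of the code. Under that condition, and with assumed opposite 5% errors at M4 and no true difference, the false ΔΔ% is about −5 to −9 points for 50% to 90% of area remaining. Knowing the visit alone, with equal proportional error on both sides and no true difference, distorts each side's Δ% but not ΔΔ%. The error sizes are illustrations; the documents give none. The change is worth making because it is cheap and closes the gap whatever the reader would in fact have seen.

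**What to change.** Amend section 2.2.1 as follows.

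- Before sheets go to the Sponsor, the site or contract organisation scans or photocopies each one under a random sheet number. Hand retracing is not used, since it would add measurement error.
- Subject, group, side, visit, lesion number and natural marks are masked on the copy. The marks stay on the site's sheet, where they are needed to find the lesion; on the reader's copy they would let sheets of one lesion be matched.
- Copies are sent in random order.
- The randomization list, product code and body drawing are withheld from the Sponsor's reader.
- One stated edge rule applies to all sheets, and the Sponsor returns one cm² value per sheet number.
- The contract organisation relinks values to subject, side and visit only after the measurement file is locked.

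The synopsis should also name the blinded roles, including this reader.

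Cost: at the minimum of 12 patients with 2 to 6 lesions and 5 visits (D0, M1 to M4), 12 × 2 × 5 = 120 to 12 × 6 × 5 = 360 tracings to copy and relabel, a linking table, and a short delay before linking. That is a few hours of clerical work. No extra reader is needed, and sample size, visits and treatment do not change.

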2.3. LESIONS EXPOSURE TO EXCIMER LAMP

The lesions will be exposed to a Quantel 308 excimer lamp that delivers a narrow UVB spectrum centered around the 308nm wavelength. This lamp makes enables to carry out phototherapy localized on the target lesion. The fluences will be performed twice a week during the whole study according to the recommendations of the French Society of Dermatology regarding phototherapy. The initial dose of 50 mJ / cm² will be increased then progressively every 2 sessions until getting a franc erythema lasting less than 48h and not causing phlyctenes.

excimer lamp Quantel 308

2.4. CUTANEOUS ACCEPTABILITY

Before (D0) and after product use (M1, M2, M3), the subjects body is examined by the dermatologist to assess each of the following parameters:

[figure not shown]
| | NONE | VERY MILD | MILD | MODERATE | SEVERE |
|----------------|--------------------------|--------------------------|--------------------------|--------------------------|--------------------------|
| Erythema |  |
| Edema |  |
| Dryness |  |
| Desquamation |  |
| Roughness |  |
| Others |  |
| Please define: | | | | | |

On D0, the subjects are also asked about their usual functional habits:

| | NONE | VERY MILD | MILD | MODERATE | SEVERE |
|-------------------------|--------------------------|--------------------------|--------------------------|--------------------------|--------------------------|
| Tightness |  |
| Stinging |  |
| Itching |  |
| Warm, burning sensation |  |
| Others |  |
| Please define: | | | | | |

At the end of the study, the cutaneous acceptability of the product is assessed by taking into account the relevant elements reported by the subject (functional and physical signs) as well as those noted during the examination (clinical signs).

The confrontation of these signs is used to conclude the final cutaneous acceptability of the studied product.

2.5. PATIENTS SCORING ON AN ANALOG VISUAL SCALE

On M4, the patient will be asked about their satisfaction with the treatment, on each side of the body:

Left side :

| | | | | | | | | | | |
|--------------------------|--------------------------|--------------------------|--------------------------|--------------------------|--------------------------|--------------------------|--------------------------|--------------------------|--------------------------|--------------------------|
|  |
| 0 | 1 | 2 | 3 | 4 | 5 | 6 | 7 | 8 | 9 | 10 |
| Not satisfied at all | | | | | | | | | | |
| Very satisfied | | | | | | | | | | |

Right side:

[figure not shown]
| | | | | | | | | | | |
|--------------------------|--------------------------|--------------------------|--------------------------|--------------------------|--------------------------|--------------------------|--------------------------|--------------------------|--------------------------|--------------------------|
|  |
| 0 | 1 | 2 | 3 | 4 | 5 | 6 | 7 | 8 | 9 | 10 |
| Not satisfied at all | | | | | | | | | | |
| Very satisfied | | | | | | | | | | |

5. APPENDICES – STUDY DOCUMENTS

5.1. RANDOMIZATION LIST (GROUPS ATTRIBUTION)

RANDOMIZATION LIST
STUDY 18E1721
17/09/2019

| ID | Groupe | Côté Droit | Côté Gauche |
|----|--------|------------|-------------|
| 1 | A | Produit A | Produit B |
| 2 | B | Produit B | Produit A |
| 3 | C | Produit A | Produit B |
| 4 | A | Produit B | Produit A |
| 5 | A | Produit B | Produit A |
| 6 | B | Produit A | Produit B |
| 7 | B | Produit B | Produit A |
| 8 | A | Produit A | Produit B |
| 9 | C | Produit B | Produit A |
| 10 | C | Produit A | Produit B |
| 11 | C | Produit B | Produit A |
| 12 | B | Produit A | Produit B |

Groupe A: 1 application/ jour (le soir) + lampe

Groupe B: 2 applications/ jour (matin et soir) + lampe

Groupe C: 2 applications/ jour (matin et soir)

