| Distribution (d) / return (r) of daily log | • (d) | • (r/d) | • (r/d) | • (r/d) | • (r/d) | • (r) | | | | | | | | | | | | | | | | | | | | | | | | | | | | | | | | | | | | | | | | | | | | | | | | | | | | | | | | | | | | | | | | | | | | | | | | | | | | | | | |
| Distribution (d) / return (r) of the studied product | • (d) | • | • | • | • | • (r) | | | | | | | | | | | | | | | | | | | | | | | | | | | | | | | | | | | | | | | | | | | | | | | | | | | | | | | | | | | | | | | | | | | | | | | | | | | | | | | |

| Foreseen dates | Product reception | Study start | Study end | 1 st results by e-mail | | |
|------------------|--|---------------|------------------|-----------------------------------|--|--|
| | October 31, 2018 | October, 2019 | May, 2020 | August, 2020 | | |
| Products | Reference | Form | Application zone | | | |
| | Product ref : 16300.04 Lot 120918A | | | | | |
| | Placebo Ref : 16300.06 Lot 120918B | | | | | |
| Study Population | Specific inclusion criteria | | | | | |
| | 
 • Sex: female and male; • Age: 18 years old and above; • Patients with stable non-segmental vitiligo lesions (defined by no new lesions or lesions existing for at least 3 months, absence of hypochromic margins in Wood's light and absence of confetti depigmentation); • Patients with 2 to 6 symmetrical lesions (1 to 3 on each side). These lesions (macules) will be treated for a minimum surface of 2 cm² and a maximum surface of 100 cm². | | | | | |
| | Number of subjects minimum 12 distributed into groups of 4 | | | | | |

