1.2. INVESTIGATIONAL PRODUCT

1.2.1. Description

| Reference | Batch# | Form | Packaging | Confidentiality procedure | Storage temperature |
|---|---------|------------------|-----------|---------------------------|---------------------|
| Product ref: 16300.04 | 120918A | Yellowish liquid | Tube | Encoded | Room temperature |
| Placebo ref: 16300.06 Lot 120918B | 120918B | Yellowish liquid | Tube | Encoded | Room temperature |

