1.2.5. Attribution to the subjects

➔ Products

Each product is attributed to volunteers according to the randomization in **Appendix 5.1**.

➔ Application zones

The application side (right/left) of the products (product/ placebo) are randomized according to the randomization list set previously.

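### Appendix 5.1 prints all 12 side allocations under one shared product code whose letters match the lot suffixes, so one guess or one unblinded patient can decode the whole list

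*Combined protocol and SAP*

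**What the plan says.** The synopsis describes a "Double blind study" and a "Comparative study, versus placebo in intra-individual", with "Number of subjects minimum 12 distributed into groups of 4". Section 1.2.5 covers both parts of the allocation. For the products: "Each product is attributed to volunteers according to the randomization in" Appendix 5.1. For the sides: "The application side (right/left) of the products (product/ placebo) are randomized according to the randomization list set previously".

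Appendix 5.1 then prints the list, dated 17/09/2019. It gives the group and the contents of the right and left side for IDs 1 to 12, for example "1 | A | Produit A | Produit B" and "9 | C | Produit B | Produit A". The appendix explains the three groups. It does not say which of Produit A and Produit B is active.

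Section 1.2.1 ties the two preparations to their batches. The product, reference 16300.04, is batch 120918A. The placebo row reads "Placebo ref: 16300.06 Lot 120918B | 120918B | Yellowish liquid | Tube | Encoded | Room temperature". The lots appear again in the synopsis and in section 1.2.2.

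The documents give no method of generating the list, no block structure, and no statement of who holds the list or the key.

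**The concern.** The product-placebo contrast is made within patients, so blinding of side carries most of the protection against assessment bias. Under section 1.3 the dermatologist traces the perimeter of every target lesion on both sides at each visit. Section 2.2.1 has the sponsor measure the area by image analysis of those tracings. If the dermatologist knows or strongly suspects the product side, the measured area inherits any bias in the drawn border.

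Two features of the list put this at risk. First, every patient's side is printed in the document that describes the trial. Second, one code covers all patients, and its letters repeat the lot suffixes that the same document assigns to product and placebo. A reader can guess the key without any unblinding event. One patient whose product side becomes clear, for example through a one-sided reaction, would confirm or correct the guess for everyone. With four patients per group and a purely descriptive analysis, a few biased tracings could move a group mean.

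**Working it through.** **Inputs.** From Appendix 5.1, the group order for IDs 1 to 12 is A B C A A B B A C C C B, and the right-side sequence is A B A B B A B A B A B A. Lots are from section 1.2.1. The planned number is 12, in groups of 4 (synopsis).

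**The list against the plan.** It holds 12 IDs, 4 per group, with 6 A and 6 B on the right. This agrees with the synopsis.

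**What the shared code gives away.** With the list in hand, the only unknown is whether A or B is the product.
- Possible readings of the list: 2.
- Readings left after one patient is unblinded: 1, so 12 of 12 patients are decoded.
- With no unblinding, the matching lot suffix suggests which reading to guess.

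**The same event under a neutral code and an undisclosed list, 2:2 within each group.**
- Possible allocations: 6 × 6 × 6 = 216.
- Allocations left after one patient is unblinded: 3 × 6 × 6 = 108.
- Each of the other 3 patients in that group has the opposite side with probability 2/3. The 8 patients in the other groups stay at 1/2.

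**The order of sides, as a secondary matter.** The side swaps at 10 of 11 successive steps; the one repeat is ID 4 to ID 5. The consecutive pairs are AB, AB, BA, BA, BA, BA, so all six are balanced. The chance of at least 10 swaps depends on the unknown method:

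| Method assumed | Chance of 10 or more swaps in 11 |
|---|---|
| Independent draws | (11 + 1)/2^11 = 12/2048 = 0.6% |
| 6:6 overall | 12/924 = 1.3% |
| 2:2 within each group, printed group order | 6/216 = 2.8% |
| Blocks of 4 in ID order | 12/216 = 5.6% |
| Blocks of 2 in ID order | (5 + 1)/2^5 = 6/32 = 18.8% |

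Under 2:2 within groups, 4 of the 11 steps join patients of the same group (swap probability 2/3) and 7 join different groups (1/2). The expected number of swaps is 4 × 2/3 + 7 × 1/2 = 6.17. All six pairs are balanced in 12 of 216 such lists (5.6%).

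**The order within groups.** Group A is ABBA, B is BABA and C is ABAB, which makes 2 + 3 + 3 = 8 swaps of 9. A 2:2 block of four has 1, 2 or 3 swaps with probability 1/3 each. The expectation is therefore 3 × 2 = 6 of 9, and 8 or more occurs with probability (1 + 3)/27 = 14.8%. That is unremarkable.

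**The case against.** A reader might infer from the order that sides were alternated rather than randomized, or that one patient's side reveals the next patient's. The documents do not support either reading.
- ABBA, BABA and ABAB are three valid draws of 2:2 blocks within groups. No text says how the list was made, and swaps were counted only after the list had been seen.
- Someone without the list would not know that the sides tend to swap. Carrying strict alternation forward from ID 1 matches only 4 of 12 rows, because of the repeat at ID 4 to 5.
- Someone with the list does not need the pattern, because one unblinded patient decodes everything.

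It is also fair to say that the blind has other protection. Both preparations are yellowish liquids in tubes and are listed as encoded (section 1.2.1). The label template in section 1.2.3 shows subject number, side and posology, with no product letter or lot. Standardized photographs are taken at the visits from D0 to M4 (section 2.1), and the sponsor measures the area. Every patient receives both products, so knowing the side cannot steer who is enrolled. The trial is a 12-patient proof of concept.

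All of this stands, and it limits the point. It does not remove it. The tubes may be well masked while the list is not. Image analysis measures a border already drawn by hand, and the plan assigns the photographs no role in checking that border.

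**Conclusion.** The weakness is one of coding and concealment. Anyone holding the protocol with its appendix has every patient's side under a two-letter code. The code has two possible readings, a plausible guess at the right one, and full disclosure of 12 of 12 after a single unblinding. The regular order adds some predictability but shows neither alternation nor a fault in generation.

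Two assumptions matter. The first is that the dermatologist has access to the protocol with Appendix 5.1; the documents do not say who holds it or describe any restriction. The second concerns the guess only: that Produit A is lot 120918A. The documents do not state this, and it should not be read as established. The single-unblinding route does not depend on it.

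The documents give no tracing error or expected effect, so the bias in cm² or in percentage repigmentation cannot be estimated. Nothing in them shows that the blind was broken. The point is worth correcting because the primary endpoint rests on blinded hand tracing and the correction is cheap.

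**What to change.** Before first inclusion:
1. Take the allocation list out of the protocol held by the site. State in section 1.2.5 how the list is generated and who holds it.
2. Replace Produit A/B with a neutral code per subject and side, such as a random tube number, unrelated to the suffixes of 120918A and 120918B. Hold the key away from the dermatologist.
3. Redraw the right/left column at random, 2:2 within each group and independently for the three groups, without disclosing the block structure to the site. A redraw is needed because the printed list is exposed: new codes on the same allocation would leave it readable.

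The cost is a reissued 12-line list and new tube codes, with no added patients or procedures. The 2:2 balance per group is kept. The remaining weakness is small. The last patient of each group is determined by the other three, and the third is determined one time in three. That averages 3 × (1 + 1/3) = 4 of 12 patients, but only for someone who knows the block structure and the true sides of the earlier patients in that group.
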